10. On dosing days, study treatment will be administered as an IV infusion over approximately 60 minutes at a slower rate during the first 15 minutes. Participants will be closely monitored at the study site for a minimum of 1 hour after completion of each infusion or until any AEs observed have resolved or stabilized, whichever is longer. For diagnostic purposes, any participant who experiences any systemic infusion-related event should have a blood sample taken ideally 30-60 minutes after the onset for tryptase testing, and samples may be analyzed by a central or local laboratory. Study sites should have access to equipment or facilities for the management of potential hypersensitivity reactions. On dosing days, study treatment infusion should be performed after other study assessments have been performed. The study site will contact participants by telephone approximately 24 hours after the infusion for general AE query.
11. EASI, IGA, and SCORAD (extent of disease and disease severity) should be performed by the investigator. Efforts should be made that the same assessor performs the assessments of a particular participant throughout the study.
12. Participants will complete a worst itch and sleep quality NRS questionnaire with a 7-day period recall immediately prior to the visit day, and questionnaires for PGIS of AD and PGIC of AD. Participants should be reminded to answer all the questions.
13. Participants will complete the DLQI questionnaire to measure how much his/her skin problem has affected his/her life over the last week. Participants should be reminded to answer all the questions.
14. On dosing days, blood sample should be taken within 60 minutes before dosing and within 10 minutes after end of infusion.
15. Serum samples will be analyzed for peripheral inflammatory markers. On dosing days, blood sample will be taken within 60 minutes before dosing.
16. Whole blood samples will be analyzed for receptor occupancy. On dosing days, blood sample should be taken within 60 minutes before dosing and within 10 minutes after end of infusion.
17. Participants who discontinue study treatment early (before completing the 4-week dosing period) should continue with all the remaining study visits. Participants who withdraw from the study any time before the Week 12 visit should complete the Week 12 (Day 85)/EOT visit at withdrawal. Participants who withdraw from study early after Week 12 should complete the Week 24 (Day 169)/EOS visit at withdrawal.

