6.9.4 Analysis of 12-Lead ECG

Summaries of 12-lead ECG parameters by visit will include:

- Descriptive statistics of actual and change from baseline.
- ECG status (i.e., normal, abnormal) summarized by a shift table
- Notable findings in ECG, which are defined as:
 - a new onset in the QT interval >500 ms
 - a new onset in the QTcF interval >500 ms
 - an increase from baseline in QTcF >60 ms
 - an increase in heart rate from baseline by $\geq 25\%$ for on-treatment values >100 bpm
 - a decrease in heart rate from baseline by $\geq 25\%$ for on-treatment values <50 bpm
 - an increase in PR interval from baseline by $\geq 25\%$ for on-treatment values >200 ms
 - an increase in the QRS interval from baseline by $\geq 10\%$ for on-treatment values >110 ms, any time on treatment.

A listing will be provided for each participant by visit.

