7.3 Analysis Visit Window

[figure not shown]
For summaries that include data collected over multiple visits, where appropriate, the data will be summarized by analysis visit window. If there are multiple measurements within a scheduled visit window (refer [Appendix 12.6](#)), the closest measurement to the scheduled timepoint of the visit will be used in the analysis. If there are two observations which have the same difference in days to the planned day, but which are not measured on the same day, the later value will be selected. If there is more than one observation on the same day then;

- Latest value will be considered in all cases except for vital signs, ECG.
- Average value will be considered in cases of continuous vital signs and ECG parameters.
- The worst value will be considered for ECG interpretation.

All measurements will be presented in the listing.

[figure not shown]

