12.6 Analysis Visit Window

Analysis Visit	Target Day	Group 1	Group 2	Group 3*	Group 4	Group 5	Group 6
Baseline	1	Up to day 1	-	Up to day 1			
Week 1	8	2-11	2-11	-	-	-	-
Week 2	15	12-22	12-22	2-22	2-22	-	2-22
Week 4	29	23-36	23-36	23-57	23-43	2-43	23-43
Week 6	43	37-50	37-50	-	-	-	-
Week 8	57	51-64	51-64	-	44-64	44-64	44-64
Week 12	85	65-92	65-92	58-127	65-92	65-92	65-92
Week 16	113	93-120	93-120	-	93-120	93-120	93-120
Week 20	141	121-148	121-148	-	121-148	121-148	121-148
Week 24	169	149-172	149-172	128-172	149-172	149-172	149-172

Group 1: Vital signs, Physical examination, Adverse events, Prior and concomitant therapies, Hematology, blood chemistry, EASI, IGA, SCORA, Itch and sleep quality NRS, PGIS, PK sampling, Receptor occupancy and TARC.

Group 2: PGIC

Group 3: Urinalysis

Group 4: Pregnancy test

Group 5: DLQI.

Group 6: ADA sampling

*Use group 3 for ECG and TB assessment by removing week 2 and week 4 and changing the Week 12 window from '58-127' to "2-127".

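### Read literally, the SAP's single Day 2-127 ECG window usually keeps unscheduled ECGs, and EOS ECGs done at withdrawal on Days 89-127, out of the notable-findings table

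*SAP*

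**What the plan says.** - **Windows.** SAP 12.6 handles ECG in a footnote to the visit-window table: "Use group 3 for ECG and TB assessment by removing week 2 and week 4", and "changing the Week 12 window from '58-127' to '2-127". This leaves Baseline, Week 12 (Days 2-127, target Day 85) and Week 24 (Days 128-172, target Day 169).
- **Selection.** Under SAP 7.3, if a window holds several measurements, "the closest measurement to the scheduled timepoint of the visit will be used in the analysis". For two records equally far from the target "but which are not measured on the same day, the later value will be selected". Same-day repeats are handled separately: "Average value will be considered in cases of continuous vital signs and ECG parameters", while the ECG interpretation takes the worst same-day value. No worst-value rule applies across days.
- **Use.** SAP 6.9.4 opens with "Summaries of 12-lead ECG parameters by visit will include" and lists notable findings beneath that line, with numeric criteria for QT, QTcF, heart rate, PR and QRS. The QRS criterion ends "for on-treatment values >110 ms, any time on treatment". Heart rate and PR are also limited to on-treatment values; QT and QTcF are not.
- **Sources of extra ECGs.** Protocol 7.2.4 lets the investigator repeat ECGs at discretion. Protocol Table 1, footnote 17 adds: "Participants who withdraw from study early after Week 12 should complete the Week 24 (Day 169)/EOS visit at withdrawal". The EOS visit includes an ECG.

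**The concern.** Table 1 schedules no ECG between Baseline and Week 12, so any ECG in that interval is unscheduled unless it belongs to an early EOT visit. Someone probably took it for a reason. Likewise, an EOS ECG recorded at an early withdrawal is the last ECG information on a person who left. These are the records that a nearest-to-target rule tends to discard when a routine Week 12 ECG is available.

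The rule suits by-visit means. It does not suit a count of people who ever crossed a safety threshold. SAP 6.9.2 treats laboratory data differently and takes the worst CTCAE grade for key parameters; ECG has no such rule across days. The SAP also disagrees with itself, because the any-time wording on QRS cannot be met by one selected record per window.

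At stake is an undercount in a safety table. SAP 9.2 also puts notable ECG findings among the outputs for the Safety Review Committee, and protocol 11.3.1 promises the proportion of participants with clinically important ECG values.

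**Working it through.** **Inputs.** ECG Week 12 window Days 2-127 (SAP 12.6). Target Day 85, visit window ±3 days, so an in-window Week 12 ECG falls on Days 82-88 (protocol Table 1). Nearest record kept, ties to the later day (SAP 7.3). Follow-up Days 86-169 (protocol 4.1). 13 participants enrolled (protocol 4.1).

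**1. Reproduce the window.** The upper limit is the midpoint of the two scheduled post-baseline ECG days: (85 + 169)/2 = 127. The lower limit is the day after baseline: 1 + 1 = 2. Midpoints also give the other urinalysis limits, (15 + 29)/2 = 22 and (29 + 85)/2 = 57. The SAP states no midpoint rule; it is inferred from the match. Length: 127 − 2 + 1 = 126 days.

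**2. Pair the Week 12 ECG with one other ECG.** For a Week 12 ECG on day s and a second ECG on day u, the second is kept only if |u − 85| < |s − 85|, or if the distances are equal and u > s. There are 126 − 1 = 125 possible days for u.

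| Week 12 ECG on Day | Second ECG kept on Days | Days on which it is dropped (of 125) |
|---|---|---|
| 82 | 83-88 | 119 |
| 83 | 84-87 | 121 |
| 84 | 85-86 | 123 |
| 85 | none | 125 |
| 86 | 85 | 124 |
| 87 | 84-86 | 122 |
| 88 | 83-87 | 120 |

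**3. EOS ECG at withdrawal.** On Days 89-127 it lies at least 89 − 85 = 4 days from target, against at most 3 for an in-window Week 12 ECG. It loses on every one of 127 − 89 + 1 = 39 days. Follow-up has 169 − 86 + 1 = 84 days, and 39/84 = 46%.

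**4. When an off-schedule ECG does enter.**
- No Week 12 ECG exists: a lone ECG on Day 20 or Day 100 is selected.
- The second ECG is nearer Day 85, or tied and later (table above).
- It falls on the same day as the selected ECG: it is averaged in.
- It is an EOS ECG at withdrawal from Day 128 on: it goes to Week 24 and is used if it is the only record there.

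For a withdrawal before Week 12, the EOT ECG can itself displace an earlier one: EOT on Day 40 is nearer Day 85 than an ECG on Day 20.

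**5. Size in the table.** One missed participant is 1/13 = 7.7%.

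**6. After the fix.** If any post-first-dose ECG counts, 0 of the 125 days are lost, and all 39 withdrawal days contribute.

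**The case against.** The strongest reply is that the SAP is ambiguous here and does not clearly exclude these records. Windowing applies only where appropriate, and the QRS wording points towards counting across records. A programmer could therefore build the table from all ECGs. That is true, but it leaves the choice until the data have been seen, and the SAP gives no instruction that settles it.

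The wide window also has a good use: it keeps in the Week 12 summary the EOT ECG of someone who withdraws before Week 12. That supports the window for by-visit statistics, not for threshold counts.

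A reader might infer more than the documents support:

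- **That these ECGs never reach the table.** Step 4 of the working shows several routes by which they do.
- **That a serious ECG result would appear in a listing only.** Protocol 8.2.3.1 requires an ECG result to be reported as an AE if it is clinically significant in the investigator's judgement, changes study treatment or leads to intervention. It would then enter the TEAE tables. The gap is confined to numeric crossings that meet none of these conditions.
- **That the primary endpoint is affected.** That endpoint is the incidence of TEAEs. ECG changes and abnormal ECG values are exploratory (protocol Table 3).
- **That half of follow-up withdrawals lose their EOS ECG.** The guaranteed loss covers 46% of follow-up days. Turning days into people assumes evenly spread withdrawals, and the documents give no withdrawal count.
- **That an ECG is expected at an infusion reaction.** The diagnostic step the protocol names is a tryptase sample; extra ECGs are discretionary.
- **That EOS urinalysis is lost in the same way.** SAP 6.9.2 also has a shift table of abnormal laboratory values during the study, not restricted by visit, so the loss is not shown.
- **That on-treatment ends at Day 85, so later ECGs fail the heart rate, PR and QRS criteria.** The visible text does not define the term, and Week 12 with its ±3 days is the EOT visit. What stands is that the term needs a definition.

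**Conclusion.** The point holds as a gap in the SAP that should be closed. Read literally, SAP 12.6, 7.3 and 6.9.4 together drop most unscheduled ECGs on Days 2-127 (119 to 125 of 125 possible days), and all EOS ECGs at withdrawal on Days 89-127, from the notable-findings summary. The any-time wording for QRS contradicts that result.

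This rests on three conditions: an in-window Week 12 ECG exists, notable findings are built from window-selected records, and the crossing is not otherwise reported as an AE. The effect is then an undercount of 7.7 percentage points per affected participant in a cohort of 13. Whether any participant was affected cannot be told from the documents. The data themselves remain in the listings.

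**What to change.** In SAP 6.9.4:

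1. Count a participant as having a notable ECG finding if any ECG after the first dose meets the criterion, including unscheduled, repeat and withdrawal-visit records. Report this as one row covering any time after the first dose.
2. Use window-selected values only for the by-visit descriptive statistics. The windows in SAP 12.6 can stay as they are.
3. Replace or define the on-treatment restriction so that heart rate, PR and QRS cover the same post-first-dose period as QTcF.

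A matching row for vital signs in SAP 6.9.3 is optional; vital signs use much narrower windows, and no comparable loss is shown there.

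The cost is SAP wording and one extra table row. No new data are needed, and the by-visit descriptive statistics do not change. The new row can exceed the by-visit counts, so a footnote should say which records it uses.

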12.7 Statistical Consideration of Intercurrent Events

[REDACTED]

12.8 CTCAE Version 5.0 for Key Hematology and Serum Chemistry Parameters

CTCAE Term	Grade 1	Grade 2	Grade 3	Grade 4	Grade 5
White blood cell decreased	<LLN - 3000/mm3; <LLN - 3.0 x 10e9 /L	<3000 - 2000/mm3; <3.0 - 2.0 x 10e9 /L	<2000 - 1000/mm3; <2.0 - 1.0 x 10e9 /L	<1000/mm3; <1.0 x 10e9 /L	-
Neutrophil count decreased	<LLN - 1500/mm3; <LLN - 1.5 x 10e9 /L	<1500 - 1000/mm3; <1.5 - 1.0 x 10e9 /L	<1000 - 500/mm3; <1.0 - 0.5 x 10e9 /L	<500/mm3; <0.5 x 10e9 /L	-
Lymphocyte count decreased	<LLN - 800/mm3; <LLN - 0.8 x 10e9/L	<800 - 500/mm3; <0.8 - 0.5 x 10e9 /L	<500 - 200/mm3; <0.5 - 0.2 x 10e9 /L	<200/mm3; <0.2 x 10e9 /L	-
Anemia	Hemoglobin (Hgb) <LLN - 10.0 g/dL; <LLN - 6.2 mmol/L; <LLN - 100 g/L	Hgb <10.0 - 8.0 g/dL; <6.2 - 4.9 mmol/L; <100 - 80g/L	Hgb <8.0 g/dL; <4.9 mmol/L; <80 g/L; transfusion indicated	Life-threatening consequences; urgent intervention indicated	Death
Platelet count decreased	<LLN - 75,000/mm3; <LLN - 75.0 x 10e9 /L	<75,000 - 50,000/mm3; <75.0 - 50.0 x 10e9 /L	<50,000 - 25,000/mm3; <50.0 - 25.0 x 10e9 /L	<25,000/mm3; <25.0 x 10e9 /L	-
Alanine aminotransferase increased	>ULN - 3.0 x ULN if baseline was normal; 1.5 - 3.0 x baseline if baseline was abnormal	>3.0 - 5.0 x ULN if baseline was normal; >3.0 - 5.0 x baseline if baseline was abnormal	>5.0 - 20.0 x ULN if baseline was normal; >5.0 - 20.0 x baseline if baseline was abnormal	>20.0 x ULN if baseline was normal; >20.0 x baseline if baseline was abnormal	
Aspartate aminotransferase increased	>ULN - 3.0 x ULN if baseline was normal; 1.5 - 3.0 x baseline if baseline was abnormal	>3.0 - 5.0 x ULN if baseline was normal; >3.0 - 5.0 x baseline if baseline was abnormal	>5.0 - 20.0 x ULN if baseline was normal; >5.0 - 20.0 x baseline if baseline was abnormal	>20.0 x ULN if baseline was normal; >20.0 x baseline if baseline was abnormal	
Blood bilirubin increased	>ULN - 1.5 x ULN if baseline was normal; > 1.0 - 1.5 x baseline if baseline was abnormal	>1.5 - 3.0 x ULN if baseline was normal; >1.5 - 3.0 x baseline if baseline was abnormal	>3.0 - 10.0 x ULN if baseline was normal; >3.0 - 10.0 x baseline if baseline was abnormal	>10.0 x ULN if baseline was normal; >10.0 x baseline if baseline was abnormal	
Creatinine increased	>ULN - 1.5 x ULN	>1.5 - 3.0 x baseline; >1.5 - 3.0 x ULN	>3.0 x baseline; >3.0 - 6.0 x ULN	>6.0 x ULN
